### **Exclusion criteria were:**

- (i) patients under the age of 18 or those incapable of giving informed consent
- (ii) Patient with premolar or molar with a pulpal diagnosis of normal pulp, previously treated, previously initiated and a periapical diagnosis of asymptomatic apical periodontitis or normal apical tissue requiring root canal therapy.
- (iii) teeth with immature apices

- (iv) teeth with apices in the maxillary sinus or those teeth where the apical lesion has eroded the bone of the maxillary sinus floor.
- (v) teeth with internal or external resorption,
- (vi) teeth with carious lesions or deficient crowns that cannot be repaired before accessing the pulp chamber.

Prior to treatment, a diagnostic exam and sensibility testing were performed. Pain data was collected at the time of presentation by having patients indicate their peak pain or discomfort level at the six-hour mark prior to root canal treatment and symptomatic apical periodontitis was confirmed by using percussion testing and a modified occlusal force meter (Occlusal Force-Meter, GM10, Nagaro Keiki, Tokyo, Japan), as demonstrated by Khan (75). The occlusal force meter numerical reading was recorded at maximal bite force prior to feeling pain on the symptomatic tooth and maximal bite force on the contralateral tooth. Pain measurements were made using a 0-100 NRS. The '0' mark represented 'no pain' and the '100' mark represented 'the worst pain imaginable'. There were 39 additional numeric markings between the '0' and '100' marks that patients could choose, and patients were instructed to write in their pain rating if it was not sufficiently represented on the scale. Along with the numeric scale, the surveys included Wong-Baker FACES as well as verbal markers indicating low, mild, moderate, high, and very high pain. For this study, scores in the very high range were considered severe pain. Scores 0-19 represented low pain, 20-39 was mild pain, 40-59 was moderate pain, 60-79 was high pain, and 80-100 was very high or severe pain.

Patients were divided into one of two treatment groups. Each treatment was scheduled for two appointments regardless of experimental group. For both groups, following confirmation of profound anesthesia, a rubber dam was placed in order to isolate the tooth in treatment. Prior to

accessing the pulp chamber, all caries, defective restorations, and deficient crowns were removed. A pre-endodontic build-up was placed if necessary, to maintain isolation. Straight-line access to the pulp orifices was then achieved. Hand files and an electric apex locator were used to determine the working length which was then verified with a periapical radiograph.

For the control (standard endodontic treatment) group, during the initial appointment the following were accomplished: Clinical exam, pre-endodontic build-up (if necessary), working length determination, all canals were instrumented using hand and rotary files to a minimum size and taper of at least 25/04 to within  $\frac{1}{2}$  to 1 mm short of the apical terminus. Between each file, 5.25% NaOCl was used to disinfect the canals and flush debris. Following instrumentation, NaOCl was ultrasonically activated for 30 seconds in each canal. Canals were then dried; UltraCal XS (Ultradent Products, Inc., South Jordan, UT) was placed into each canal measured 2mm short of working length. A spacer of either sterile cotton pellet or sterile sponge were placed followed by an interim restoration of either Cavit or Glass ionomer to a minimum thickness of 3.5mm.

In the experimental group during the initial appointment the following were accomplished: Clinical exam, pre-endodontic build-up (if necessary), working length determination, all canals were instrumented using hand and rotary files to a maximum size and taper of 20/07 to 1 mm short of the apical terminus. Between each file, 5.25% NaOCl was used to disinfect the canals and flush debris. Following instrumentation of the canals, Kool-dam heatless liquid dam was used to build an occlusal platform that functioned to support the GWS handpiece and seal the access opening during treatment. For molars, included gauges were used to determine the proper handpiece attachment. The GWS handpiece was positioned on the tooth for the entirety of the GWS treatment, which varied in length of time depending on the pulpal diagnosis of the tooth. The canals were then dried using paper points and UltraCal XS (Ultradent Products, Inc., South

Jordan, UT) was placed into each canal measured 2mm short of working length. A spacer of either sterile cotton pellet or sterile sponge were placed followed by an interim restoration of either Cavit or Glass ionomer to a minimum thickness of 3.5mm. Once the temporary restoration was completed, patients were given the same 0-100 NRS pain assessment to take home and were asked to record their level of pain at 6, 24, 72, and 168 hours post-treatment. In order to control any pain that may have been unbearable, patients were educated on the ibuprofen and acetaminophen regimen introduced by Menhinick et al 2004 (92) and instructed to record how much was taken.

Patients then returned for a second appointment 2-4 weeks after the initial visit. Pain data was collected at the time of presentation by having patients indicate their peak pain or discomfort level at the six-hour mark prior to the appointment. The occlusal force meter numerical reading was recorded at maximal bite force prior to feeling pain on the symptomatic tooth and maximal bite force on the contralateral tooth. Pain measurements were made using a 0-100 NRS-41. Patients were anesthetized, teeth isolated with rubber dam, access was re-established by removing the interim restorative material and intracanal medicament. The appropriate final canal size was determined by the treating clinician and between each file, 5.25% NaOCl was used to continue to disinfect the canals and flush debris. Following instrumentation, NaOCl was ultrasonically activated for 30 seconds in each canal, each canal was then flushed with 17% EDTA for 1 minute followed by a rinse of 5.25% NaOCl. A final rinse of 95% ethanol was used for all sealers except for those made of bioceramic materials. Canals were then dried and filled with gutta-percha and the clinician's sealer of choice. In order to control any pain that may have been unbearable, patients were educated on the ibuprofen and acetaminophen regimen introduced by Menhinick et al 2004 and instructed to record how much was taken.

### **Statistical Method**

NRS pain scores were compared between treatment groups at each post-operation time point (6, 24, 72, 168 hours) using linear mixed-effects models with fixed effects for treatment, time, treatment-by-time interaction, and pre-operation NRS pain score, and a random effect for participant to account for within-participant correlation of longitudinal measurements.

Categorical NRS pain scores were compared using mixed-effects logistic regression models with fixed effects for treatment, time, treatment-by-time interaction, and pre-operation NRS pain score category, and a random effect for participant. Mechanical allodynia bite force was compared between treatment groups using the two sample t-test. Mechanical allodynia bite force was compared between treated and control teeth within each treatment group, and between visit 1 and visit 2 in treated teeth within each treatment group, using the paired t-test. Age category, sex, pulpal diagnosis, tooth type, and visit 2 NRS pain category were compared between groups using the chi-square test for association. Continuous measures are summarized using means with 95% confidence intervals. Categorical measures are summarized using rates. Analyses were conducted using R version 4.0.3.

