## **Research Design**

This study was a single-blind, randomized, controlled clinical trial comparing the incidence and severity of postoperative pain and mechanical allodynia following root canal treatment. Based on a similar previous study (81), a sample size of 38 patients (19 per group) was necessary to achieve a power of 80%. Following a standard endodontic cleaning and shaping protocol, the independent variables are (1) conventional side-vented needles for irrigant delivery combined with ultrasonic activation and (2) irrigation using the Gentlewave system. Five 2nd year residents in the Graduate Endodontics division at the University of Minnesota School of Dentistry performed all treatments. The target population of the study included patients of the Graduate Endodontics clinic requiring root canal treatment.

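### SAP, Statistical Method: the between-arm bite-force t-test names no visit or tooth; on its natural reading it is valid but leaves the recorded visit-1 value unused

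*SAP*

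**What the plan says.** The SAP's Research Design describes a trial "comparing the incidence and severity of postoperative pain and mechanical allodynia following root canal treatment". At the first appointment, before treatment, "The occlusal force meter numerical reading was recorded at maximal bite force prior to feeling pain on the symptomatic tooth", together with "maximal bite force on the contralateral tooth". The same two readings are described at the next appointment: "Patients then returned for a second appointment 2-4 weeks after the initial visit". Four values per patient are therefore available (two teeth, two visits).

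The Statistical Method section uses them in three ways:

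- Between arms: "Mechanical allodynia bite force was compared between treatment groups using the two sample t-test". No visit, tooth or covariate is given.
- Within arm, between teeth: "Mechanical allodynia bite force was compared between treated and control teeth within each treatment group". Teeth are named, but no visit.
- Within arm, between visits: "between visit 1 and visit 2 in treated teeth within each treatment group, using the paired t-test". Tooth and visits are both named.

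For pain, the same section fits a linear mixed model with "fixed effects for treatment, time, treatment-by-time interaction, and pre-operation NRS pain score, and a random effect for participant". The model for categorical pain scores likewise includes the pre-operation category.

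The protocol does not fill the gap. Its Study Summary and section 5.2 mention the force meter only before treatment, the data list in 5.2 omits bite force, and section 15 has no bite-force analysis.

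**The concern.** The between-arm sentence could refer to any of the four recorded values, or to a change or a between-tooth difference. Only the treated tooth at visit 2 is a reading of the treated tooth after the arms diverged. A visit-1 test compares baselines, and a contralateral test compares untreated teeth. The reader therefore has to infer what is being tested in the only between-arm comparison of mechanical allodynia that the SAP describes.

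On the natural reading a second point follows. The visit-1 force on the same tooth is already recorded but does not enter the test. With about 19 patients per arm, chance differences in starting bite force can be appreciable, and an unadjusted t-test does not correct for them. If the two visits are at least modestly correlated, precision is lost as well. The SAP takes the opposite approach for pain and gives no reason for the difference.

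**Working it through.** **Inputs.** SAP, Research Design: 38 patients, 19 per group, 80% power. Protocol 15.2: 17 per group, 80% power for a difference of 1 SD. Protocol 15.3: significance level 0.05 (stated for the pain tests; assumed here for bite force, and assumed two-sided). Protocol 10.1: 1:1 allocation. Not in the documents: the correlation r between visit-1 and visit-2 bite force. The values 0, 0.3, 0.5 and 0.7 are assumptions. Normal data and a visit-2 SD of 1 are assumed.

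**The plan's own figures.** Exact two-sample t-test power for a 1 SD difference is 78.1% at 16 per group and 80.7% at 17, so the protocol's 17 reproduces. The SAP's 19 cannot be derived, because no effect size or SD is given. It corresponds to 80% power at 0.934 SD.

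**Variance of the treatment difference.**

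- t-test on visit-2 values: 2/n, with n = 19.
- ANCOVA, given the observed baseline imbalance: (1 - r²)(2/n)(1 + D), where D = T²/36 and T follows a t distribution on 36 df.
- Mean of T² is 36/34, so the mean of 1 + D is 1 + 1/34 = 35/34 = 1.0294.
- Ratio, ANCOVA to t-test: (1 - r²) × 35/34.

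Results at 19 per arm. Power is from the noncentral t (36 df for the t-test, 35 df for ANCOVA), integrated over D:

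| | t-test | ANCOVA r = 0 | r = 0.3 | r = 0.5 | r = 0.7 |
|---|---|---|---|---|---|
| 1 - r² | – | 1 | 0.91 | 0.75 | 0.51 |
| Variance ratio | 1 | 1.029 | 0.937 | 0.772 | 0.525 |
| Change in variance | – | +2.9% | -6.3% | -22.8% | -47.5% |
| Difference detectable with 80% power (SD) | 0.934 | 0.948 | 0.905 | 0.821 | 0.677 |
| Power at 0.934 SD | 80.0% | 78.8% | 82.5% | 89.0% | 97.1% |
| Power at 0.6 SD (illustrative) | 43.7% | 42.6% | 46.0% | 53.5% | 69.9% |

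**Break-even.** Setting (1 - r²) × 35/34 = 1 gives r = √(1/35) = 0.169. In general r = √(1/(N - 3)), so the threshold depends on the total N: √(1/31) = 0.180 at N = 34, √(1/97) = 0.102 at N = 100 and √(1/147) = 0.082 at N = 150. The last two are the protocol's recruitment figures.

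**Simulation check (60,000 trials per setting, N = 38).** ANCOVA power at 0.6 SD was 0.429, 0.458, 0.534 and 0.698 for the four values of r. Type I error was 0.049 to 0.051 for both methods.

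**Change score, for comparison.** With equal variances at the two visits, its variance relative to the visit-2 t-test is 2(1 - r), which is 2.0, 1.4, 1.0 and 0.6. It beats the visit-2 test only when r exceeds 0.5, and at each of these values it is less precise than ANCOVA.

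**The case against.** The strongest reply is that the t-test is valid, holds its 5% level, and needs no correlation to justify it. Nothing in the documents shows that r is large. There is some reason for doubt: visit 1 is read on teeth confirmed as symptomatic and visit 2 comes weeks after canal treatment, so in patients whose pain has resolved the later reading may reflect bite strength more than a pain threshold. This stands as a limit on the size of the gain. It is not a case against adjusting, because the worst loss is about 1 point of power.

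A reader might infer that the SAP definitely discards the visit-1 value. The text does not establish this. With no visit named, the sentence could cover both visits, with visit 1 as a check of comparability; the section also compares age, sex, diagnosis and tooth type between groups. A change score cannot be excluded either. The omission follows only on the visit-2 reading.

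A reader might also infer that the between-arm sentence is a lone lapse beside fully specified paired tests. It is not: one of the two paired comparisons also names no visit.

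Finally, the SAP summarises continuous measures by means with 95% confidence intervals. If that includes visit-1 bite force, an imbalance would be visible, though still not corrected.

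**Conclusion.** The point holds as a modest, inexpensive improvement. The visit and tooth are missing from the between-arm test, and the visit is missing from the treated-versus-control test. On the natural reading (treated tooth, visit 2) the t-test is valid but leaves out a recorded baseline that the SAP's own pain models would use.

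At N = 38, adjustment gains little at r = 0.3 (about 2 points of power) and becomes material from about r = 0.5 (9 points where the t-test has 80%). Below r = 0.17 it is slightly worse. These figures rest on the assumed r, normal data, a linear relation, and complete bite-force data in 19 patients per arm.

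The documents do not support a reading in which the t-test is biased or the trial's main conclusion is at risk. Protocol sections 3.1 and 3.2 define the endpoints as occurrence and intensity of pain, so bite force is a supporting measure and the pain comparison is untouched. Nor is there any argued defect in the within-arm paired tests beyond the one unnamed visit.

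**What to change.** Replace the between-arm sentence with, for example: *For bite force on the treated tooth at visit 2, the arms were contrasted by ANCOVA with terms for arm and visit-1 bite force on that tooth; the adjusted mean difference is given with its 95% confidence interval.* State the visit for the treated-versus-control-tooth paired test.

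The SAP is written in the past tense and names its R version, so the analysis has probably been done. In that case, keep the t-test as reported, state which visit and tooth it used, and show the ANCOVA beside it, labelled post hoc.

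Naming the visits and tooth costs nothing. The ANCOVA needs no new data. It costs one degree of freedom and, if r is near 0, about 1 point of power (80.0% to 78.8% at 0.934 SD; 43.7% to 42.6% at 0.6 SD).

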## 15. Statistical Considerations

15.1. Data Analysis: To examine the research question, a two-sample t test will be conducted to determine if mean differences exist on post-operative pain

following treatment with the Gentlewave system and post-operative pain following standard endodontic treatment. Two-sample t test, with a significance level of 0.05, is an appropriate statistical analysis if each of the two samples can be matched on the pain measurements at 6, 24, 72, and 168 hours following the completion of treatment. A linear mixed effects model will be used to compare the groups across time. Also, descriptive statistics will be used for patient demographics and characteristics.

- 15.2. Power Analysis: A sample size of 17 per group will give an 80% power to detect a mean difference between the two groups of 1 standard deviation. This sample size selection and power analysis is based off of previous studies
- 15.3. Statistical Analysis: A two-sample t-test will be used with a significance level of 0.05 for pain measurements recorded at 6, 24, 72, and 168 hours. A linear mixed effects model will be used to compare the groups across time. Also, descriptive statistics will be used for patient demographics and characteristics.
- 15.4. Quality control of the collected data will be overseen by the principal investigator.

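### The within-arm visit 1 to visit 2 bite-force tests cannot show an effect of Gentlewave, and the one between-arm bite-force test names no visit and states no adjustment for the visit-1 value

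*SAP*

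**What the plan says.** The SAP's Research Design states a comparative aim: incidence and severity of postoperative pain and mechanical allodynia under two irrigation methods, with 19 patients per group.

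The bite-force reading is described in the text after the exclusion criteria: "The occlusal force meter numerical reading was recorded at maximal bite force prior to feeling pain on the symptomatic tooth". A maximal reading is also taken on the contralateral tooth. Both readings are repeated at visit 2: "Patients then returned for a second appointment 2-4 weeks after the initial visit". The same meter has a diagnostic role: "symptomatic apical periodontitis was confirmed by using percussion testing and a modified occlusal force meter". No force cut-off is given.

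The SAP's Statistical Method then lists these bite-force analyses:
- Between arms: "Mechanical allodynia bite force was compared between treatment groups using the two sample t-test". It does not say whether this uses visit 1, visit 2 or the change, and it states no covariate.
- Within each arm: treated against control teeth, and "between visit 1 and visit 2 in treated teeth within each treatment group, using the paired t-test".

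For NRS pain, by contrast, the same section uses a model with "fixed effects for treatment, time, treatment-by-time interaction, and pre-operation NRS pain score, and a random effect for participant". The SAP does not say which bite-force test carries the treatment conclusion, and does not label the within-arm tests as descriptive.

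**The concern.** The only bite-force analysis explicitly defined as visit 1 to visit 2 is an uncontrolled before-after test, run once in each arm. Between the two readings both arms have canal instrumentation, hypochlorite irrigation, an intracanal dressing (calcium hydroxide in Protocol section 5.2), the same analgesic advice and 2-4 weeks of natural course. There is no untreated arm. Some rise in the pain-free bite force is therefore to be expected whichever irrigation was used.

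Two such tests say nothing about the difference between arms. If one is significant and the other is not, it is easy to write that allodynia resolved under one technique only. If both are significant, that does not favour Gentlewave either. The comparative answer has to come from the two-sample test, and that test is under-specified: it could be run on visit 1, visit 2 or the change, and as written it leaves the collected visit-1 reading unused as a covariate.

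**Working it through.** **1. The plan's own figures.** The documents give no power statement for bite force. For pain, Protocol section 15.2 says: "A sample size of 17 per group will give an 80% power to detect a mean difference between the two groups of 1 standard deviation". Check with a two-sided two-sample t-test, alpha 0.05, d = 1. At n = 17 the noncentrality is √(17/2) = 2.915 on 32 df, giving power 80.7%. At n = 16 it is √(16/2) = 2.828 on 30 df, giving 78.1%. So 17 is reproduced. The SAP's 19 per group cannot be reproduced, because no effect size is stated.

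**2. Inputs for the within-arm tests.**
- n = 19 per arm (SAP, Research Design).
- Alpha 0.05. The protocol gives this level for pain only, "A two-sample t-test will be used with a significance level of 0.05 for pain measurements recorded at 6, 24, 72, and 168 hours"; the SAP gives none for bite force. Two-sided is assumed.
- Standardised paired change dz (mean change divided by SD of change): not in the documents, assumed range 0 to 1.2, identical in both arms.

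**3. Chance that exactly one arm is significant when the arms do not differ.** Let p be the chance that one arm shows a significant improvement, from the noncentral t with 18 df and noncentrality dz × √19. The arms are independent, so P(exactly one) = 2p(1−p) and P(Gentlewave only) = p(1−p).

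| dz | p | Exactly one arm | Gentlewave only |
|---|---|---|---|
| 0 | 0.025 | 4.9% | 2.4% |
| 0.2 | 0.128 | 22% | 11% |
| 0.30 | 0.235 | 36% | 18% |
| 0.47 | 0.492 | 50% | 25% |
| 0.60 | 0.696 | 42% | 21% |
| 0.68 | 0.800 | 32% | 16% |
| 0.80 | 0.909 | 17% | 8% |
| 1.0 | 0.984 | 3% | 1.5% |
| 1.2 | 0.999 | 0.3% | 0.1% |

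For example, at dz = 0.60: 2 × 0.696 × 0.304 = 0.42.

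**4. A between-arm test in the same situation.** In simulation (40,000 runs, 19 per arm, same true change in both arms), a two-sample test on the visit-2 value or on the change rejected in 4.8% to 5.2% of trials across all scenarios.

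**5. Regression to the mean.** If entry kept the lowest fraction q of baseline readings, and the two visits correlate at ρ, the expected rise with no true change is (1−ρ) × φ(z_q)/q SD. Both q and ρ are assumptions. The last two columns are for 19 per arm.

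| q | ρ | Rise (SD) | Significant, per arm | Exactly one arm |
|---|---|---|---|---|
| 0.3 | 0.5 | 0.5 × 0.348/0.3 = 0.58 | 75% | 37% |
| 0.5 | 0.7 | 0.3 × 0.399/0.5 = 0.24 | 27% | 39% |
| 0.9 | 0.9 | 0.1 × 0.175/0.9 = 0.02 | 4% | 7% |

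**6. What adjustment for visit 1 buys.** Assume equal variance at both visits and a linear relation. Relative to an unadjusted visit-2 comparison (variance 1), a change score has variance 2(1−ρ) and ANCOVA has 1−ρ². At ρ = 0.5, 0.7 and 0.9 the change score gives 1.00, 0.60 and 0.20; ANCOVA gives 0.75, 0.51 and 0.19. ANCOVA is lower than both in each case, apart from the one degree of freedom it uses.

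**7. Subtracting the contralateral tooth.** With equal variances, the variance of the difference of two changes is 2(1−r) times that of one change, where r is the correlation between the two teeth's changes. That is a gain only if r > 0.5, and no value is given. The two readings also differ in kind: force before pain on one tooth, maximal force on the other.

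**The case against.** The strongest reply is that the comparative test is already there. The SAP sentence just before the paired tests plans a two-sample comparison of bite force between arms. Randomisation protects it: recovery and regression to the mean act on both arms alike, and its error stays near 5%. This stands. A reader might infer from the paired tests that the plan has no between-arm evidence on allodynia; that would be wrong.

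Nor does the SAP say that a claim about Gentlewave rests on within-arm change. A reader might infer that natural recovery will be reported as a treatment effect. The documents do not support that forecast; whether bite tenderness eases after root canal treatment is a legitimate descriptive question.

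It is also tempting to say that visit-1 readings were selected to be low, so that regression to the mean must inflate the rise. Eligibility is by diagnosis, percussion was used alongside the meter, Protocol section 5.2 records biting force in addition to pain on percussion, and no cut-off, SD or correlation is given. The effect may be negligible or large.

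Finally, the one-arm-only risk is small if the true change is nil or large, and half of it falls on the control arm. Bite force is not an endpoint in Protocol section 3, and the pain models are unaffected.

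What remains is that the paired tests are not marked as descriptive, and the between-arm test lacks a stated visit and a baseline adjustment.

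**Conclusion.** The concern holds in a limited form. The within-arm paired tests cannot answer the comparative question set in the SAP's Research Design. The test that can answer it is planned but not fully specified, and is not adjusted in the way the NRS model is.

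The size is conditional. It applies only if the paired tests are read as a comparison of arms. Then, with 19 per arm, two-sided 0.05 and equal true change, a one-arm-only result arises in about 17% to 50% of trials for dz from 0.3 to 0.8, and about 3% at 1.0, against about 5% for a between-arm test. The true dz is unknown. The general point does not depend on any assumed selection on bite force: any improvement shared by both arms makes a within-arm rise uninformative about Gentlewave.

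**What to change.** In the SAP, Statistical Method:

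1. Make the between-arm comparison of visit-2 bite force on the treated tooth, adjusted for its visit-1 value (ANCOVA, difference with 95% CI), the test of treatment for allodynia.
2. Report the visit 1 to visit 2 change in each arm as a mean with 95% CI, descriptive only, without a test.
3. State that no claim about Gentlewave rests on within-arm change.
4. Optionally add the contralateral reading as a covariate or in a sensitivity analysis. It need not be subtracted.

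The SAP is written in the past tense, so report this analysis openly as re-specified and keep the originally planned two-sample result available beside it.

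The cost is a few sentences of SAP text and one model on readings the plan already collects at both visits. The downside is that two within-arm p-values are no longer reported as tests.

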## 10. Local Number of Participants

10.1. Local Number of Participants to be Consented: The approximate number of participants requested is 150. 34, or 17 per treatment group, is the lowest number that will give an 80% power to detect a mean difference between the two groups of 1 standard deviation. ([name] and [name] will each analyze a subcategory of symptomatic patients: Necrotic symptomatic teeth or Vital symptomatic teeth). Requesting 150 participants allows for greater clinical meaningfulness and accounts for possible dropouts. Randomization order for each arm of the study will be 1 to 1.

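### Visit-2 pain is recorded on the 0-100 NRS but tested only as a category by an unadjusted chi-square, which gives up roughly 40-60% of the ANCOVA power at 19 per arm under assumed values and five bands

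*SAP*

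**What the plan says.** **Before treatment.** The SAP (text after the exclusion criteria) has patients "indicate their peak pain or discomfort level at the six-hour mark prior to root canal treatment", on a 0-100 NRS. It defines five bands: 0-19, 20-39, 40-59, 60-79 and 80-100.

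**Second appointment.** The SAP collects the same peak-pain rating, again at the six-hour mark before the appointment: "Pain measurements were made using a 0-100 NRS-41". Bite force up to the onset of pain is also recorded at this visit.

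**Analysis (SAP, Statistical Method).** The linear mixed model on the NRS score covers 6, 24, 72 and 168 hours and includes "pre-operation NRS pain score, and a random effect for participant". The logistic mixed model for categorical NRS adjusts for pre-operative NRS category. Bite force is analysed as a continuous measure by t-tests, including visit 1 against visit 2. Visit-2 NRS is named once, after age category, sex, pulpal diagnosis and tooth type: "visit 2 NRS pain category were compared between groups using the chi-square test for association".

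**Size.** The SAP (Research Design) states that "a sample size of 38 patients (19 per group) was necessary to achieve a power of 80" percent, and gives no effect size or SD.

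**The concern.** Visit-2 pain is measured after allocation and after the first-visit irrigation, so it is an outcome. The SAP handles it like a patient characteristic. Three things are lost:

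- **The score.** A 0-100 rating is reduced to bands, and the chi-square test then ignores all differences within a band.
- **The baseline.** The same rating was taken before treatment, and the SAP uses it as a covariate in its other NRS comparisons.
- **The estimate.** A chi-square test gives a p-value but no between-arm difference in NRS points.

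At 19 per arm the loss of power can be large. A non-significant chi-square could then be read as no difference at visit 2 when the test had little chance of showing one. Sparse cells add to this: in the simulations below, the five-band chi-square rejected in only about 3-4% of trials with no true effect, against a nominal 5%.

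**Working it through.** **1. The plan's own figure.** The SAP's 19 per group cannot be reproduced, because no effect size or SD is given. The protocol's figure can. Its section 15 gives 17 per group for "80% power to detect a mean difference between the two groups of 1 standard deviation", at level 0.05 (two-sided assumed). The normal approximation is n = 2(1.96 + 0.84)²/1² = 15.7, so 16 per arm. The exact t-test needs 17, with power 80.7%. At 19 per arm, 1 SD has 85.1% power, and 80% power corresponds to 0.934 SD.

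**2. Inputs for visit 2.** From the documents: 19 per arm, 1:1 allocation ("Randomization order for each arm of the study will be 1 to 1", protocol section 10), level 0.05 and five bands. Assumed, because the documents give none of them: control mean 15-40, SD 20-22, pre/post correlation ρ = 0.3-0.5, pre-operative mean 55 and SD 25, latent shift 15 or 20 points. Scores are rounded to 2.5 (a 41-point scale) and limited to 0-100.

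**3. What the shifts mean on the recorded scale.** Truncation at 0 shrinks them. The recorded mean of a normal score cut at 0 is μΦ(μ/σ) + σφ(μ/σ). With σ = 20:
- control, μ = 15: 15(0.773) + 20(0.301) = 17.6
- shift of 15, μ = 0: 20(0.399) = 8.0, a recorded difference of 9.6
- shift of 20, μ = -5: -5(0.401) + 20(0.387) = 5.7, a recorded difference of about 12

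Across the assumed range, latent shifts of 15 and 20 give recorded differences of about 10-14 and 12-18 points.

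**4. Simulated power, 19 per arm.**

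| Test at visit 2 | Latent shift 15 | Latent shift 20 |
|---|---|---|
| Chi-square, five bands | 24-27% | 40-45% |
| t-test on score | 50-56% | 73-78% |
| ANCOVA with pre-operative score | 53-63% | 75-86% |

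Relative loss is 1 - power(chi-square)/power(ANCOVA). Pairing the ends of the ranges gives 1 - 27/53 = 49% to 1 - 24/63 = 62% for the smaller shift, and 1 - 45/75 = 40% to 1 - 40/86 = 53% for the larger. Together that is roughly 40-60%.

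**5. Where the loss comes from.** Take control mean 25, SD 22, ρ = 0.5 and a shift of 20. The powers are 0.41 (chi-square), 0.73 (t-test) and 0.81 (ANCOVA), a loss of 1 - 0.41/0.81 = 49%. Of the 0.40 gap, 0.73 - 0.41 = 0.32 is banding and 0.81 - 0.73 = 0.08 is baseline adjustment. Across the scenarios, adjustment adds about 0-3 points of power at ρ = 0.3 and 6-11 at ρ = 0.5.

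**6. Sensitivity.**
- Two-level category cut at 20: loss about 21-46% without continuity correction, about 40-65% with R's default correction.
- Effect 1 SD, control mean 30-60, five bands: chi-square 51-57%, ANCOVA 81-98%, loss about 32-46%.
- Effect 0.934 SD with many scores near 0 (control mean 5-10, ρ = 0.3-0.5): chi-square 22-30%, ANCOVA 62-74%, loss about 57-66%.
- Effect 0.5 SD: loss about 51-76%.

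**The case against.** **The number of bands is not stated for visit 2.** The SAP defines five, but analyses categorical NRS elsewhere by logistic regression, which is usually a two-level model. A two-level category is plausible and the loss can then be much smaller. This stands. A reader might infer that half the power is lost as a fact of the plan, but the documents supply no mean, SD, correlation, effect or number of bands that would fix the figure.

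**Visit 2 is not a designated endpoint.** The protocol names the occurrence of post-operative pain as primary and its intensity as secondary (section 3), and analyses pain at 6, 24, 72 and 168 hours (section 15). The SAP already uses a baseline-adjusted model on the score at those times. This stands and limits the weight of the point. Nothing here weakens the 6-168 hour analysis.

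**Visit-2 NRS is not the only later pain measure.** That is a tempting inference, but bite force to pain is also recorded at visit 2, and the protocol (section 5.2) plans a further NRS record for 168 hours after the final appointment.

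**Baseline adjustment matters less than banding.** This also stands. No document gives the pre/post correlation, and treatment and 2-4 weeks lie between the two ratings, so the covariate cannot be assumed to be strong.

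**Means are reported anyway.** The SAP summarises continuous measures by means with 95% CIs. That could describe visit-2 NRS within each arm, but no between-arm difference is promised.

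None of this gives a reason to prefer the banded, unadjusted test. The t-test row shows most of the gain without relying on any correlation.

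**Conclusion.** The point holds as one of efficiency and consistency. The SAP repeats the pre-operative rating at visit 2, then tests it only as a category, with no covariate, among patient characteristics. At 19 per arm, the loss against ANCOVA is roughly 40-60% with the five bands the SAP defines. It is about 21-46% for a two-level cut at 20 without continuity correction, and about 40-65% with that correction. These figures rest on the assumed means, SDs, correlations and shifts listed above, and most of the loss is due to banding.

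A reader might go further and conclude that a real benefit at visit 2 would usually be missed. The documents do not support that as a general statement. At 1 SD, the only effect size they give, five-band chi-square has 51-57% power away from the floor of the scale. At the smaller shift, ANCOVA itself misses 37-47% of real effects. The change is worth making, but the trial's main pain comparisons do not depend on it.

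**What to change.** In the SAP, Statistical Method:

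- Analyse the visit-2 0-100 NRS score by ANCOVA with treatment and pre-operative NRS score. Report the adjusted between-arm difference with its 95% CI.
- Keep the visit-2 bands as a descriptive table by arm, and state how many bands it uses.
- Remove visit-2 NRS from the sentence on patient characteristics.
- The SAP is written in the past tense. If results are already known, label the added analysis accordingly.

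The cost is one SAP sentence and one model. Both scores are already collected, and no change to sample size or visits is needed.
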